7.3 HANDLING OF MISSING DATA

For primary efficacy endpoint and other endpoints which are continuous in nature, the use of a restricted maximum likelihood (REML)-based mixed model repeated measures (MMRM) approach, if feasible, will ensure that missing data are handled implicitly, via a missing at random assumption, by the statistical model.

For efficacy endpoints which are binary nature, a Non Response Imputation (NRI) approach will be applied to the missing visits up to Week 12; that is, imputing as a failure to achieve a response in the visits with missing endpoint score, however:

- If there are available data at the visits both before and after the visit with a missing outcome, then impute as a success only if both the preceding and the following measurement indicate success and no rescue medication has been given during this period.
- Otherwise, impute as a failure to achieve a response (i.e. no response imputation)

NRI is a conservative imputation scheme because it assumes that use of rescue therapy or missing data due to any other reason is related to treatment failure. In addition, for secondary binary endpoint, HiSCR at Week 12, multiple imputation based method will be applied as sensitivity analysis.

Further sensitivity analyses to assess the robustness of the results on efficacy endpoint will be described in the TSAP if necessary.

With respect to safety evaluations, it is not planned to impute missing values.

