6.3 SUBJECT SETS ANALYSED

The following analysis sets will be defined for this trial:

Enrolled Set (ES)

This patient set includes all patients who signed informed consent. It will be used for analyses of patient disposition.

Randomized Set (RS):

This patient set includes all randomized patients. Treatment assignment will be as randomized.

Safety Analysis Set (SAF):

This patient set includes all patients who were randomized and received at least one dose of study drug. This is the main analysis set for efficacy and safety. Patients will be analyzed according to the actual treatment received.

Per-Protocol Set (PPS):

This patient set includes all patients in the randomized set who adhered to the CTP without any iPDs which are flagged for exclusion from the PPS in the table above. The PPS will be used for sensitivity analysis on the primary endpoint.

The discussion of all exceptional cases and problems and the decisions on the allocation of patients to populations will be made at latest at the RPM/DBLM.

Handling of Treatment Misallocations in Analysis Sets

If a patient is randomized but not treated, they will not be reported under their randomized treatment group for efficacy and safety analysis according to PPS, and SAF.

If a subject is treated but not randomized, they will be excluded from the efficacy analysis and safety analysis by definition. However, subjects under such circumstances will be described in the final clinical trial report.

If a subject is randomized but takes incorrect treatment during the study, then:

- For efficacy and safety analyses using the SAF which are based on actual treatment:
 - If a subject is planned to receive administration of Spesolimab (randomized to Speso), then they will be reported under the Spesolimab group if the subject receives at least 1 vial of randomized Spesolimab.
 - If a subject is planned to receive placebo treatment, then they will be reported under the placebo arm if they are treated and receive no vial of randomized Spesolimab. If the subject receives ≥ 1 vial of randomized Spesolimab, then the patient will be handled differently for efficacy analysis and safety analysis. It will keep as placebo for efficacy reporting. For safety, then the patient will be reported as treated with Spesolimab treatment group.

Proprietary confidential information © 2021 Boehringer Ingelheim International GmbH or one or more of its affiliated companies

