Table 6.3: 1 Overview of use of patient analysis sets by class of endpoint and handling of estimand and missing data

Class of Endpoints	ES	RS	SAF	PKS	PPS
Disposition	OR	OR			
Compliance and exposure			OR		
iPD		OR			
Demographic/baseline characteristics		OR	OR		
Concomitant medication		OR			
Primary endpoint			EC-H-MMRM EC-H-MMRM ¹ EC-H-MMRM ⁴ EC-S-MMRM ¹ OC ² , OC-IR ²		EC-H-MMRM ¹
Secondary binary efficacy endpoints			EC-H-NRI, EC-H-NRI ¹ EC-H-NRI ⁴ OC ² EC-H-MI ³		
Secondary continuous efficacy endpoints			EC-H-MMRM EC-H-MMRM ¹ EC-H-MMRM ⁴ EC-S-MMRM ³ OC ²		
Further efficacy endpoints			Binary: EC-H-NRI Continuous: EC-H-MMRM ¹ All: OC ² ,		
Concentration & ADA			OR	OR	
Safety data			OR OC-IR		

¹ sensitivity/further analysis

² descriptive display only

³ selected endpoints.

⁴ subgroup analysis

For explanation of the different approaches with regard to missing data see [Section 6.6](#).

[figure not shown]
EC-H: Hybrid strategy by implementing estimand concept. Any data post rescue medication use will be censored.

EC-S: Supplementary strategy by implementing estimand concept. Any data collected after use of any rescue therapy or restricted medication are censored.

OC = observed cases excluding values after any use of rescue medication.

OC-IR = observed cases including also values after any use of rescue medication.

OR = original results.

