6.6.2 Efficacy data

Based on the different reasons for patients' data missing for different endpoints, various approaches will be used to assess the impact of missing data on the efficacy endpoints of this trial, depending upon the type of the endpoint (cf. [Table 6.3: 1](#)). Approaches to be applied are described below.

Proprietary confidential information © 2021 Boehringer Ingelheim International GmbH or one or more of its affiliated companies
Missing data imputations will be performed using all available on-treatment data observed up to the respective analysis cut-off date, if applicable.

Some efficacy endpoints are defined with a particular binary outcome, i.e. Achievement of PGA score of 0 or 1. Then imputation is planned to take place only at the binary level, i.e., the PGA score itself as a ordinal variable will not be imputed, but the binary endpoints derived based on these scores will be imputed, unless otherwise specified.

Continuous efficacy endpoints

For efficacy endpoints which are continuous in nature, the use of a restricted maximum likelihood (REML)-based mixed effect model with repeated measures (MMRM) approach, if applicable, will ensure that missing data are handled implicitly, via a missing at random assumption, by the statistical model.

In addition, the efficacy endpoints during randomized treatment period may be displayed descriptively using following methods:

- Observed cases (OC) approach will include all collected data, without imputation for any missing data. Such an OC approach will exclude all values measured after intake of a rescue therapy.
- Observed cases (OC-IR) approach will include all collected data, without imputation for any missing data. Such approach will be used as a sensitivity method for data display and is an extension of the OC approach which includes additionally all values which were measured after rescue therapy. Will also include all values measured after any use of investigator prescribed SoC.

Binary efficacy endpoints

Primary Imputation Approach – No Response Imputation [NRI]:

For all binary endpoints (i.e. endpoints that are either 1 (patient responded) or 0 (patient did not respond)), the following will be performed as the primary imputation approach (analysis type):

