- If there are data at visits both before and after the visit with a missing outcome, then impute as success only if both neighbouring visits also represent a success (independent of whether the preceding and following observations were selected for analysis based on time windows described in [Section 6.7](#) and no rescue treatment has been given during this period).
- Otherwise, impute as a failure.

Other Imputation Approaches:

- OC method will be also used to display the binary data.
- Multiple Imputation (MI) approach:
For selected secondary binary endpoint, i.e., achievement of HiSCR at Week 12, multiple imputation (MI) will be used to handle missing data as a sensitivity analysis. Use baseline and on-treatment data only and impute HiSCR as binary variables with values 0, 1. The

Proprietary confidential information © 2021 Boehringer Ingelheim International GmbH or one or more of its affiliated companies
imputation will be done using OC data as the input dataset, and will follow the steps outlined below:

1. *Multiple Imputation of Missing data:* use SAS procedure PROC MI with the Fully Conditional Specification (FCS) method and corresponding options/statements (SAS manual). Discriminant function method is used to impute missing values by using the ordering of the class level in each variable.

```
PROC MI DATA= hiscr_mi2 seed= 136852 nimpute=100 out=mi_fcs;  
CLASS HiSCR_base- HiSCR_12 trt stratum;  
VAR HiSCR_base- HiSCR_12 trt stratum;  
FCS DISCRIM (HiSCR_base- HiSCR_12 trt stratum /CLASSEFFECTS=include);  
RUN;
```

Note that the seed 136852 will be used throughout. If a second seed is required, 136853 will be used, and so on as necessary.

2. *Analysis of Completed Datasets:* The imputed complete dataset will be used to calculate the response rate for each arm. The risk difference will be also calculated together with the standard error based on the normal approximation.
3. *Combine Results:* Separate approach will be applied to the combination of the response rate for each arm and the difference between them.
 - For the response rate of each arm, the distributions are not expected to be approximately normal, so Rubin's rules (13) should not be used. Instead, the point estimate will be calculated as the mean of individual imputations and the 95% confidence interval for each arm will implement the MIWilson(14) approach.

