7.5 SECONDARY ENDPOINT(S)

7.5.1 Key secondary endpoint(s)

This section is not applicable as no key secondary endpoint has been specified.

7.5.2 (Other) Secondary endpoint(s)

For each of the secondary endpoint described below, hybrid strategy will be used to handle intercurrent events which lead to data censoring as described for the primary endpoint.

Continuous secondary endpoints

The continuous secondary endpoints up to Week 12 will be analysed using a MMRM approach based upon the model specification as described for the primary endpoint.

Additionally, subgroup analysis will be performed for variables as described in [Section 6.4](#).

Binary secondary endpoints

The binary secondary endpoints will be evaluated descriptively by treatment arm via frequency tables (with 95% confidence interval based on the Wilson score for each group and based on the Chan and Zhang method for risk difference). As in the case of the primary estimand, any binary data collected after use of any rescue therapy will be censored and then imputed using the NRI method as described in CTP section 7.3 “Handling of Missing Data”.

Example SAS code for CI of proportion difference by Chan and Zhang method is as follows:

```
PROC FREQ DATA=data;  
<WHERE treat IN ('Treatment_1','Treatment_2') ;>  
TABLES treat*endpoint_bin / RELRISK RISKDIFF.  
EXACT RELRISK (METHOD=SCORE column=2) RISKDIFF (METHOD=SCORE  
column=2);  
RUN;
```

For selected binary endpoint, e.g., achievement of HiSCR at Week 12, following additional analyses are planned.

Logistic regression analysis

Proprietary confidential information © 2021 Boehringer Ingelheim International GmbH or one or more of its affiliated companies
The difference in the proportion of patients with a response between Spesolimab and placebo will be analysed using predictive margins in a binary logistic model via %Margins in SAS®. Fixed classification effects will include treatment and stratification factor (TNFi-naive population versus TNFi-failure population).

Example SAS code:

```
%Margins(data= data,  
class    = treat stratum,  
response = endpoint_bin,  
roptions = event='1',  
dist     = binomial,  
model    = treat stratum,  
margins  = treat,  
options  = cl diff)
```

Stratified risk difference

[figure not shown]
A Mantel-Haenszel type weighted average of differences will be implemented with corresponding Wald confidence intervals based on the variance formula provided by Sato.

[figure not shown]
Example SAS code:

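### Do the binary endpoints need their own analysis that censors after restricted medication (EC-S)?

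*SAP*

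**What the plan says.** The footnotes to SAP Table 6.3:1 define two censoring strategies. The main one is "EC-H: Hybrid strategy by implementing estimand concept. Any data post rescue medication use will be censored". The wider one is "EC-S: Supplementary strategy by implementing estimand concept. Any data collected after use of any rescue therapy or restricted medication are censored".

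The table enters EC-S-MMRM for the primary endpoint (as a sensitivity or further analysis) and for selected continuous secondary endpoints. Binary secondary endpoints have EC-H-NRI, OC and, for selected endpoints, EC-H-MI. Further binary endpoints have EC-H-NRI and OC. No binary row contains EC-S.

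The text agrees with the table:

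- **Main binary analysis.** SAP 7.5.2 states that "any binary data collected after use of any rescue therapy will be censored and then imputed using the NRI method". Protocol 7.3 states that "a Non Response Imputation (NRI) approach will be applied to the missing visits up to Week 12".
- **Observed cases.** Table 6.3:1 has "OC = observed cases excluding values after any use of rescue medication", and SAP 6.6.2 adds "Such an OC approach will exclude all values measured after intake of a rescue therapy".
- **Multiple imputation for HiSCR.** In SAP 6.6.2 the "imputation will be done using OC data as the input dataset".
- **Per-protocol set.** SAP 6.3 limits its role: "The PPS will be used for sensitivity analysis on the primary endpoint".

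Protocol 2.1.1 sets the comparison of interest for every efficacy objective as one without the effects of rescue. Protocol 7.2.3 carries this over to the binary endpoints.

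**The concern.** The sponsor evidently thought restricted medication could disturb the results, because EC-S was planned for the primary and selected continuous endpoints. SAP Table 6.2:1 itself describes deviation D2.01 as use that may influence efficacy data. HiSCR, PGA 0/1, NRS30 and elimination of draining fistulas have no such check, and the visible text gives no reason for the difference.

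NRI does not fill the gap, because it acts only on missing visits. A patient who takes a restricted HS treatment without meeting the worsening criterion, and who is then seen at Week 12 as a responder, is counted as a responder. Either arm could be credited with a response reached on medication that the protocol does not allow. With 15 placebo patients, one such case is visible in the percentage.

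**Working it through.** **1. Which analyses keep the response**

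| Analysis of binary endpoints | Censors after | Week 12 response observed after restricted, non-rescue medication |
|---|---|---|
| EC-H-NRI (main) | rescue | stays a response |
| OC | rescue | unclear |
| EC-H-MI (HiSCR) | as OC, its input | unclear |

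The two unclear entries come from SAP 6.6.2. It describes OC-IR as OC extended by values after rescue, and adds that OC-IR also takes in values after standard of care prescribed by the investigator. This suggests that plain OC leaves those values out. HS medication started outside the rescue rule could well be such care. So only EC-H-NRI certainly keeps the response.

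**2. Which medication is affected**

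Protocol 4.2.2.2 defines rescue broadly, as treatment for disease worsening, and names systemic antibiotics and biologics. Antibiotics given for worsening but for too long (second part of D2.03) are therefore already censored. Antibiotics before Week 4 (D2.02), or a biologic, given for real worsening can also meet that definition, although the documents do not settle this. What remains is medication that is restricted and not rescue. Examples are HS antibiotics without worsening, corticosteroids for HS, and opioids.

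**3. When it can reach a Week 12 endpoint**

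Protocol 3.3.4.1 names immunosuppressants, systemic corticosteroids for HS, opioids and off-rule HS antibiotics among the reasons to stop trial drug. Protocol 3.1 and 6.2.3 then bring the end-of-treatment visit forward, and the Flowchart schedules no lesion counts after it. Week 12 is then missing with no later visit, and NRI sets it to failure.

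Three routes stay open:

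- a start between the last dose (Day 71) and Week 12 (Day 85), which is 14 of 84 days;
- a patient who keeps attending visits after stopping drug;
- topical corticosteroids for HS or topical cannabis oil, which are restricted in Table 4.2.2.1:1 but not named in 3.3.4.1, whose list is only illustrative.

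**4. Size of one case**

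Inputs: 30 and 15 patients (protocol synopsis). For illustration, placebo response is 4/15 = 26.7%, within the 26% to 28% in protocol 1.1. The spesolimab figure of 15/30 is an assumption.

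- One patient: 1/15 = 6.7 points; 1/30 = 3.3 points.
- Main analysis: 15/30 − 4/15 = 23.3 points.
- One placebo responder reclassified: 15/30 − 3/15 = 30.0 points.
- One spesolimab responder reclassified: 14/30 − 4/15 = 20.0 points.
- Standard error of the difference: √(0.5 × 0.5/30 + 0.267 × 0.733/15) = √(0.00833 + 0.01304) = 14.6 points.
- Wilson 95% interval for 4/15: 10.9% to 52.0%.

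**5. How often**

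The documents give no rate. Assume that a share p of patients starts such medication at a constant rate over 84 days, and that a share c of those who start in the last 14 days turn from non-responder to responder. The share starting in that window is w = 1 − (1 − p)^(14/84). The chance of at least one start among 45 is 1 − (1 − w)^45. The chance of at least one conversion is 1 − (1 − wc)^45.

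| p (assumed) | w | At least one start | At least one conversion, c = 10% to 25% (assumed) |
|---|---|---|---|
| 2% | 0.34% | 14.1% | 1.5% to 3.7% |
| 5% | 0.85% | 31.9% | 3.8% to 9.1% |
| 10% | 1.74% | 54.6% | 7.5% to 17.8% |
| 20% | 3.65% | 81.2% | 15.2% to 33.8% |

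These figures cover the 14-day route only. The other two routes would add to them by an unknown amount.

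**6. The plan's own figure**

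The 80.1% in protocol Table 7.5:1 concerns the continuous primary endpoint alone. It reproduces: SE = 45 × √(1/30 + 1/15) = 14.23, and Φ((42 − 30)/14.23) = 80.0%. It does not depend on how binary data are censored.

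**The case for a change.** The case for a change is a reasonable one. The omission can be read straight from Table 6.3:1. The per-protocol set would drop D2.01 to D2.03 patients but is not applied to binary endpoints. An EC-S-NRI analysis, run only if such an event occurs, would need SAP wording and a little programming. Medication start dates are already collected and the deviations are already reviewed by hand. Fixing the rule before unblinding is cleaner than choosing it afterwards, and case-by-case rulings at the database lock meeting (SAP 6.2) do not replace a stated analysis.

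What stands is that EC-H-NRI keeps such a response, and that the topical products widen the route beyond the last 14 days. What does not stand is that every binary analysis keeps it, since OC and the imputation built on it may not.

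Nor would the case be hidden. SAP 6.2 summarises and lists important deviations, SAP 7 lists all individual values, and SAP 7.2 summarises concomitant medication. In 45 patients a responder on restricted medication can be found and the rate recounted by hand. HiSCR and PGA also rest largely on the same lesion counts as the primary endpoint, for which EC-S and per-protocol analyses are planned.

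The extra analysis would also gain little for pain. Protocol 4.2.2.4 allows non-opioid analgesics to be started or increased, so NRS30 would still carry analgesic effects. EC-S is itself optional for the primary endpoint under SAP 7.4.2.

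**Conclusion.** No change is needed. The main binary analysis does what the protocol's estimand asks: it removes the effects of rescue and nothing else. The missing entry is one supplementary analysis of mainly descriptive secondary endpoints, in a trial that protocol 7.1 declares exploratory. Leaving it out is a fair trade-off, and analysts can make good the gap from data and listings already planned.

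One affected responder shifts a rate by 6.7 points on placebo or 3.3 on spesolimab, less than half of the 14.6-point standard error in the illustration. The direction is unknown. For the 14-day window, the chance of at least one converted patient runs from 1.5% to 33.8% over the assumed ranges.

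This rests on three things: the assumed rates of use and conversion; the early end-of-treatment rule being followed; and the visible footnotes giving the full censoring rule. SAP 5.4.5, 5.4.6 and 10.1, which hold the event and endpoint definitions, are not in the public text. They may already settle how OC treats standard of care and how early antibiotics or biologics are classed.

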6.5 POOLING OF CENTRES

No analysis is planned to explore the effect of individual centres; all centres will be pooled for analysis.

6.6 HANDLING OF MISSING DATA AND OUTLIERS

Section 7.3 of the CTP describes the handling of missing data.

The original results (OR) approach implies the presentation of data exactly as observed (not using time windows and not setting values to missing).

OR analysis will be performed on parameters and endpoints that are either not affected by patients' rescue therapy use (e.g., plasma concentration level of spesolimab, rescue therapy itself), or it is not meaningful to apply any imputation rule for the replacement of missing values.

6.6.1 Withdrawals

The reasons for withdrawal from treatment will be reported as indicated on the eCRF.

6.6.2 Efficacy data

Based on the different reasons for patients' data missing for different endpoints, various approaches will be used to assess the impact of missing data on the efficacy endpoints of this trial, depending upon the type of the endpoint (cf. [Table 6.3: 1](#)). Approaches to be applied are described below.

Proprietary confidential information © 2021 Boehringer Ingelheim International GmbH or one or more of its affiliated companies
Missing data imputations will be performed using all available on-treatment data observed up to the respective analysis cut-off date, if applicable.

Some efficacy endpoints are defined with a particular binary outcome, i.e. Achievement of PGA score of 0 or 1. Then imputation is planned to take place only at the binary level, i.e., the PGA score itself as a ordinal variable will not be imputed, but the binary endpoints derived based on these scores will be imputed, unless otherwise specified.

Continuous efficacy endpoints

For efficacy endpoints which are continuous in nature, the use of a restricted maximum likelihood (REML)-based mixed effect model with repeated measures (MMRM) approach, if applicable, will ensure that missing data are handled implicitly, via a missing at random assumption, by the statistical model.

In addition, the efficacy endpoints during randomized treatment period may be displayed descriptively using following methods:

- Observed cases (OC) approach will include all collected data, without imputation for any missing data. Such an OC approach will exclude all values measured after intake of a rescue therapy.
- Observed cases (OC-IR) approach will include all collected data, without imputation for any missing data. Such approach will be used as a sensitivity method for data display and is an extension of the OC approach which includes additionally all values which were measured after rescue therapy. Will also include all values measured after any use of investigator prescribed SoC.

Binary efficacy endpoints

Primary Imputation Approach – No Response Imputation [NRI]:

For all binary endpoints (i.e. endpoints that are either 1 (patient responded) or 0 (patient did not respond)), the following will be performed as the primary imputation approach (analysis type):

- If there are data at visits both before and after the visit with a missing outcome, then impute as success only if both neighbouring visits also represent a success (independent of whether the preceding and following observations were selected for analysis based on time windows described in [Section 6.7](#) and no rescue treatment has been given during this period).
- Otherwise, impute as a failure.

Other Imputation Approaches:

- OC method will be also used to display the binary data.
- Multiple Imputation (MI) approach:
For selected secondary binary endpoint, i.e., achievement of HiSCR at Week 12, multiple imputation (MI) will be used to handle missing data as a sensitivity analysis. Use baseline and on-treatment data only and impute HiSCR as binary variables with values 0, 1. The

Proprietary confidential information © 2021 Boehringer Ingelheim International GmbH or one or more of its affiliated companies
imputation will be done using OC data as the input dataset, and will follow the steps outlined below:

1. *Multiple Imputation of Missing data:* use SAS procedure PROC MI with the Fully Conditional Specification (FCS) method and corresponding options/statements (SAS manual). Discriminant function method is used to impute missing values by using the ordering of the class level in each variable.

```
PROC MI DATA= hiscr_mi2 seed= 136852 nimpute=100 out=mi_fcs;  
CLASS HiSCR_base- HiSCR_12 trt stratum;  
VAR HiSCR_base- HiSCR_12 trt stratum;  
FCS DISCRIM (HiSCR_base- HiSCR_12 trt stratum /CLASSEFFECTS=include);  
RUN;
```

Note that the seed 136852 will be used throughout. If a second seed is required, 136853 will be used, and so on as necessary.

2. *Analysis of Completed Datasets:* The imputed complete dataset will be used to calculate the response rate for each arm. The risk difference will be also calculated together with the standard error based on the normal approximation.
3. *Combine Results:* Separate approach will be applied to the combination of the response rate for each arm and the difference between them.
 - For the response rate of each arm, the distributions are not expected to be approximately normal, so Rubin's rules (13) should not be used. Instead, the point estimate will be calculated as the mean of individual imputations and the 95% confidence interval for each arm will implement the MIWilson(14) approach.
 - For the risk difference, the distribution is approximately normal, so Rubin's rules can be used. Accordingly, PROC MIANALYZE is used to combine the analysis results from step 2 and generate valid statistical inferences by accounting for the variability introduced by the MI process.

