5.2.2 Secondary endpoint(s)

[figure not shown]
Secondary Endpoints at Week 12 are defined as described below:

[figure not shown]
- Percent change from baseline in draining fistula count at Week 12
(Only patients with at least one draining fistula at baseline will be used for analysis).
- Achievement of Hidradenitis Suppurativa Clinical Response (HiSCR) at Week 12. HiSCR is defined as at least a 50% reduction in the total AN count with no increase in abscess count and no increase in draining fistula count relative to baseline.
- Absolute change from baseline in International Hidradenitis Suppurativa Severity Score System (IHS4) value at Week 12
- Absolute change from baseline in HASI score at Week 12
- Achievement of PGA score of 0 or 1 at Week 12
- Achievement of at least 30% reduction from baseline in Numerical rating scale (NRS30) in Patient's Global Assessment of HS Pain at Week 12
- Occurrence of complete elimination of draining fistulas at Week 12
(Only patients with at least one draining fistula at baseline will be used for analysis).
- Occurrence of at least one flare (defined as at least 25 % increase in AN count with a minimum increase of 2 relative to baseline) up to Week 12
- Absolute change from baseline in DLQI Score at Week 12
- Absolute change from baseline in HiS-QoL Total Score at Week 12

[figure not shown]
See [Section 10.1](#) for further details regarding endpoint definition and derivation.

The following safety endpoint is also defined:

- The occurrence of Treatment Emergent Adverse Events (TEAEs)

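### Does non-response imputation turn missing flare assessments into flare-free outcomes?

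*SAP*

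**What the plan says.** SAP 5.2.2 lists ten secondary efficacy endpoints, five of them binary. Four of the five are favourable events: HiSCR, PGA 0 or 1, NRS30 and complete elimination of draining fistulas. The fifth is unfavourable and cumulative: "Occurrence of at least one flare (defined as at least 25 % increase in AN count with a minimum increase of 2" lesions over baseline, at any time up to Week 12.

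The imputation rule in SAP 6.6.2 covers every binary endpoint and is written in responder terms: "For all binary endpoints (i.e. endpoints that are either 1 (patient responded) or 0 (patient did not respond)), the following will be performed". When a missing visit has data on both sides, the SAP says "then impute as success only if both neighbouring visits also represent a success", provided no rescue was given in between. The default is "Otherwise, impute as a failure".

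Protocol 7.3 has the same scope: "For efficacy endpoints which are binary nature, a Non Response Imputation (NRI) approach will be applied to the missing visits up to Week 12". It calls the method conservative on the ground that rescue use or "missing data due to any other reason is related to treatment failure".

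SAP Table 6.3:1 assigns NRI under the hybrid estimand strategy to the secondary binary endpoints and lists no exception for flare. It also lists an observed-case display for them. Multiple imputation is specified for HiSCR only. SAP 5.2.2 sends the reader to Section 10.1 for endpoint derivation; that section is not in the public copy.

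**The concern.** The responder language fits four of the five binary endpoints without thought. For flare, the event named in the endpoint is the bad outcome. A programmer who codes the named event as 1, and takes non-response imputation to mean setting missing values to 0, would record an unobserved visit as flare-free. A patient leaving at Week 2 with no flare seen by then would count as flare-free to Week 12, and an arm losing more patients in that state would look better. The opposite coding gives the opposite result. With 30 and 15 patients, a few such cases would visibly move the flare rates and their difference.

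**Working it through.** **1. Read the rule with each coding of flare.**

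| Patient's data | Success = flare-free (the SAP's terms) | Flare coded 1, missing set to 0 |
|---|---|---|
| Flare observed at any visit, then data missing | flare | flare |
| Missed visit between two flare-free visits, no rescue | no flare | no flare |
| Missed visit next to a visit with a flare | flare (already observed) | flare (already observed) |
| No flare observed, data stop before Week 12 | flare | no flare |

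At patient level the codings part only in the last row, apart from the rescue case in step 3. A dropout with a flare on record is not counted as a success under either.

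**2. Which coding does the text support?** SAP 6.6.2 defines 1 as a patient who responded, not as an event that occurred. The rule itself runs on success and failure. Protocol 7.3 ties missing data to treatment failure. A flare is not a response or a success, so the default branch gives a flare. The flare-free result requires replacing responded by event occurred, which neither document does.

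**3. Are rescued patients affected?** Inputs: worsening is a 150% increase in AN count (Protocol 4.2.2.2); baseline AN count is at least 5 (inclusion criterion 7); a flare is an increase of at least 25% and at least 2 lesions.

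- Read as an increase by 150%: 1.5 × 5 = 7.5 lesions at the smallest baseline, above 2 lesions and above 0.25 × 5 = 1.25.
- Read as an increase to 150%: 0.5 × 5 = 2.5, so at least 3 whole lesions, again above both limits.

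Both margins grow with baseline. A patient whose worsening count is recorded before rescue already has a flare under either coding.

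**4. Size of the gap between the codings.** The documents give no flare rate and no dropout rate, and Protocol 7.5 assumes complete data for the primary endpoint. There is therefore no planned figure to reproduce for flare; Table 7.5:1 concerns the primary endpoint and is untouched. With the planned arms (30 and 15):

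shift in an arm's flare rate = (patients with incomplete data and no observed flare) / n

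- Placebo: 1/15 = 6.7 points per such patient.
- Spesolimab: 1/30 = 3.3 points per such patient.

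Illustrations with assumed counts:

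| Observed flares (spesolimab, placebo) | Incomplete, no flare seen | Missing = no flare | Missing = flare | Change in difference |
|---|---|---|---|---|
| 6/30, 3/15 | 3, 0 | 20.0% v 20.0% | 30.0% v 20.0% | +10 points |
| 6/30, 3/15 | 6, 0 | 20.0% v 20.0% | 40.0% v 20.0% | +20 points |
| 6/30, 3/15 | 0, 3 | 20.0% v 20.0% | 20.0% v 40.0% | −20 points |
| 6/30, 3/15 | 6, 3 | 20.0% v 20.0% | 40.0% v 40.0% | 0 |

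With 4/15 placebo and 3/30 spesolimab patients of this kind, the arm rates differ between codings by 26.7 and 10.0 points, and the risk difference by 26.7 − 10.0 = 16.7 points. For scale, the Wilson 95% interval around 6/30 runs from 9.5% to 37.3%.

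These figures measure the distance between two readings. They are not the size of an error in the plan.

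**The case for a change.** The best case for a change is that the visible text never names the favourable flare outcome, although SAP Section 3 says the document specifies the analyses in full. Fistula elimination is also phrased as an occurrence, which invites coding the named event as 1 for both. The SAP does not say how a visit-level rule maps to a cumulative endpoint; under the conservative coding, one missed Week 12 visit makes a flare case. Early discontinuers have no scheduled lesion counts after their EoT visit, and some discontinuation triggers in Protocol 3.3.4.1, such as needing systemic antibiotics for HS before Week 4, suggest worsening. The observed-case display is not a clean opposite bound, because SAP Section 7 bases percentages on all patients in the set. The direction is also better fixed before unblinding.

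The silence on coding and on the cumulative mapping stands, as far as the public text goes. The rest carries less weight. Section 10.1 is where such a derivation belongs, and its absence from the public copy cannot be held against the plan. Protocol 3.1 and 6.2.3 bring early discontinuers to an EoT visit as soon as possible, and the Flowchart schedules lesion counts there. A patient who stops because of worsening should therefore have a count that records the flare under either coding. Bias towards the arm with more dropout needs worsening that is never recorded.

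**Conclusion.** No change to the plan follows. Read in its own terms, the rule treats flare-free as the success and a missing visit as a failure, which agrees with the protocol's rationale. A rule written specially for flare would mostly repeat the two existing branches and the observed-case display already planned. The one substantive addition would be to declare every early leaver without an observed flare a flare case. The default branch already gives that result, and it is a debatable choice because it can overstate flares.

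What remains is a coding detail that an analyst settles when deriving the endpoint. A wrong choice would cost 6.7 points per affected placebo patient and 3.3 per affected spesolimab patient, on one of ten secondary efficacy endpoints, none of them key (SAP 5.2.1). Binary secondary endpoints are summarised descriptively, and Protocol 7.1 rules out confirmatory testing.

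The conclusion assumes that responded and success carry their ordinary meaning, that EoT lesion counts are taken from early discontinuers as scheduled, and that the unseen Section 10.1 does not code flare the other way.
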